In addition to its role as a diagnostic biomarker, serum VEGF-D is also a prognostic as well as a predictive biomarker. In the MILES trial, the baseline serum VEGF-D levels were similar in the placebo and treatment arms (12). Baseline serum VEGF-D levels correlated with multiple markers of disease severity, including pneumothorax, bronchodilator responsiveness and need for supplemental oxygen, and with physiologic parameters such as FVC ( $p=0.002$ ), total lung capacity (TLC ( $p<0.0001$ )) and diffusion capacity for carbon monoxide ((DLCO) ( $p<0.0001$ )). Higher baseline serum VEGF-D levels were also associated with disease progression and treatment response. Each 1-unit increase in baseline log (VEGF-D) was associated with a baseline to 12-month change of -70 cc in the placebo group and +70cc in the sirolimus group ( $p<0.001$ ). Placebo patients with baseline VEGF-D levels  $\geq 600$ pg/ml were found to decline much faster than the placebo patients with VEGF-D  $< 600$ pg/ml, and the  $\geq 600$ pg/ml sirolimus group patients responded better than the sirolimus patients with VEGF-D  $< 600$ pg/ml. While VEGF-D levels remained stable in the placebo arm, treatment with 12 months of sirolimus resulted in approximately 50% reduction in the mean VEGF-D levels. In the observation year, VEGF-D values remained stable in the placebo group, but increased again in the sirolimus group (Figure 2). Sirolimus induced reduction in serum VEGF-D was highly correlated with improvement in lung function. Improvement in baseline-to-12-month FEV1 occurred in 65% of VEGF-D responders (patients with a VEGF-D decrease  $\geq 42\%$  from its baseline value), as opposed to only 27% of VEGF-D non-responders ( $p=0.04$ ) (Figure 3). These data indicate that VEGF-D is a clinically useful prognostic biomarker of disease progression and a predictive biomarker of treatment response (16). Similar findings have been replicated in another analysis (17). Similarly, reduction in serum

[figure not shown]
VEGF-D by approximately 50% was noticed after treatment with open-label everolimus in a recent trial (Figure 4) (18). These findings suggest that serum VEGF-D can serve as a biomarker to monitor the response to treatment in patients with LAM. Since LAM cells are the source of elevated VEGF-D, monitoring VEGF-D levels as treatment response can also serve as a surrogate for LAM cell burden and activity.

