### **5.2 Inclusion Criteria:**

Subjects enrolled in the trial must meet **all** of the following criteria.

1. Definitive diagnosis LAM based on the presence of characteristic cystic change on high-resolution computed tomography (HRCT) of the chest. The diagnosis must be confirmed by one of the following:
  - A) Histopathological confirmation by biopsy (lung, abdominal mass, lymph node or kidney or cytology from thoracic or abdominal sources revealing HMB45+ staining of spindled/epithelioid cells)
  - B) Compatible chest CT scan findings in the setting of tuberous sclerosis, angiomyolipomas (diagnosed by CT, MRI by the site radiologist or biopsy) or chylous pleural effusion (verified by tap)
  - C) Chest CT scan findings compatible with LAM and a VEGF-D level  $\geq$  800pg/ml.
2. Age 18 years or greater
3. Signed and dated informed consent
4. Currently on sirolimus for treatment of LAM for at least 20 weeks
5. Evidence of disease stabilization on sirolimus as demonstrated by two stable values of serum VEGF-D post initiation of sirolimus drawn at least 12 weeks apart from each other. For the purpose of this study, a variation in serum VEGF-D of less than or equal to 15% is considered stable.

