## 15. Statistical considerations:

*Sample size determination:* As mentioned previously, the mean serum VEGF-D level prior to treatment was approximately 2,000pg/ml in both the MILES trial (12) as well as the everolimus trial (18). In both studies, treatment with mTOR inhibitors resulted in an almost 50% reduction in the serum VEGF-D levels (12, 18). Since patients in our study will be on sirolimus prior to enrolment, we estimate that the starting serum VEGF-D level in our study will be approximately 1,000pg/ml. The largest change between serial VEGF-D levels in the placebo group of MILES was 42%. Thus, VEGF-D responders in MILES trial were conservatively defined as patients in whom serum VEGF-D decreased to a value greater than 42% from its baseline (16). Accordingly, we made our power calculations based on the ability to show a greater than or equal to 42% change in serum VEGF-D levels. Assuming the correlation between the baseline and subsequent VEGF-D levels is 0.7, a sample size of 20 subjects will provide 80% power to detect a mean VEGF-D difference from baseline to post-treatment of 420pg/ml or higher with the level of significant of 0.05 and a standard deviation of 800 for the difference. Allowing for a 20% dropout rate, we expect to recruit 25 patients for our study. Sample size calculations were done using SAS version 9.4.

*Data Analysis:* The analysis will be based on an intention to treat design. All subjects that receive study drug will be included in the safety and efficacy analysis set. The primary analysis will occur after the last enrolled participant has completed the 24-week visit. All analyses will be performed using SAS version 9.4. A p-value less than 0.05 will be considered as statistically significant.

**Specific Aim #1:** To determine if combined resveratrol and sirolimus leads to reduction in serum VEGF-D compared to VEGF-D reduction on sirolimus alone. Paired t-test will be performed to detect the difference of serum VEGF-D after 24 weeks of treatment with the serum VEGF-D prior to enrolment. The response variable VEGF-D will be measured repeatedly, at baseline and at weeks 8, 16, and 24. The change from baseline to the other study time points will indicate the treatment effect with resveratrol and sirolimus.

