Initially, by using the paired t-test we will test whether these effects are statistically significant. Multivariate linear regression models will be used to assess the relationship between serum VEGF-D change and the covariates including patient's clinical or demographic factors. Linear mixed models will be performed to detect the correlation between serum VEGF-D and the covariates taking into account the correlation between repeated measurements within the same patient. A repeated measures ANOVA model and linear mixed models will be performed to compare the serum VEGF-D at follow-up visits to the baseline taking into account the correlation between repeated measurements within the same patient.

**Specific Aim #2:** To determine the safety and adverse effect profile of combined resveratrol and sirolimus in LAM. Subjects will be evaluable for safety if they have received at least one dose of the study drug. The frequency, severity and duration of all adverse events, regardless of cause, will be recorded on the case report forms. The frequency and severity of adverse events will be calculated by patient, with each patient counted once using the most severe grade experienced. The duration of adverse events

will be calculated by the number of days each event persisted. Adverse events will be tabulated by body system and by severity using the NCI Common Terminology Criteria for Adverse Events (CTCAE) v4.0, which can be obtained from the CTEP website: <http://ctep.cancer.gov/reporting/ctc.html>. Tables will be generated for all adverse events including those that are judged to be possibly, probably or definitely related to the drug. In order to assess the safety and adverse effect profile of resveratrol in LAM, we will assign a binary indicator variable to indicate a patient with or without adverse events. A multivariable logistic regression model will be used to assess of the effect of the covariates on the probability of having adverse events for patient with LAM. All interested factors will be adjusted in the logistic regression model. Model selection will be based on stepwise criterion when appropriate.

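### VEGF-D is tested with no transformation: a likely loss of efficiency for falls below 42%, not a validity error; separately, the SD of 800 is mislabelled and as written gives 61% power, not 80%

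*Combined protocol and SAP*

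**What the plan says.** Section 15, Specific Aim #1, and the synopsis (Data Analysis) give the primary test: "Paired t-test will be performed to detect the difference of serum VEGF-D after 24 weeks of treatment with the serum VEGF-D prior to enrolment". Regression and longitudinal models follow: "A repeated measures ANOVA model and linear mixed models will be performed to compare the serum VEGF-D at follow-up visits to the baseline". No scale is named for any of them, and no transformation, check or alternative is given for VEGF-D. The raw scale is implied by the power target of 420 pg/ml from a starting level of about 1,000 pg/ml.

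The same documents describe VEGF-D in percentages:
- Planned effect (Section 15): "Accordingly, we made our power calculations based on the ability to show a greater than or equal to 42% change in serum VEGF-D levels".
- Stability at entry (Section 5.2): "a variation in serum VEGF-D of less than or equal to 15% is considered stable".
- Reference variation (Section 15): "The largest change between serial VEGF-D levels in the placebo group of MILES was 42" per cent.

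The sample size paragraph, repeated in the synopsis, states 80% power with 20 subjects. It begins "Assuming the correlation between the baseline and subsequent VEGF-D levels is 0.7" and ends "with the level of significant of 0.05 and a standard deviation of 800 for the difference".

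**The concern.** If a positive marker is right-skewed and treatment lowers it by a similar percentage in everyone, the mean pg/ml change is dominated by the few patients with the highest levels. A paired t-test on raw values then has less power than one on logs, and the result leans on a handful of people. Patients enter already stable on sirolimus, so an added effect below 42% is plausible, and that is where a loss would matter. In an open-label, single-arm trial of 20 evaluable patients, choosing the scale after seeing the data would also weaken the primary result.

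The power sentence raises a second question: whether 800 can be the SD of the difference, as labelled, and still give 80% power.

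**Working it through.** **Step 1: the plan's own figure.** Inputs from Section 15: difference 420 pg/ml, n = 20, alpha 0.05 (two-sided assumed; the plan does not say), SD 800, correlation 0.7. Paired t-test power uses the noncentral t with df = 19 and noncentrality 420 × √20 / SD of difference.
- 800 as the SD of the difference, as labelled: 420 × 4.472 / 800 = 2.35, power 60.6%; 31 patients needed for 80%. A one-sided test does not rescue it (73.2%; 24 needed).
- 800 as the SD at each visit: SD of difference = 800 × √(2 × (1 − 0.7)) = 620; 420 × 4.472 / 620 = 3.03, power 82.0%; 20 is the smallest n reaching 80%.

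Only the second reading reproduces the plan. Allowing for 20% dropout, 20 / 0.8 = 25 agrees.

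**Step 2: skew.** Under that reading levels have mean 1,000 and SD 800. A normal distribution would put Φ(−1,000/800) = Φ(−1.25) = 10.6% of values below zero, which is impossible for a concentration. Right skew is therefore likely. The documents give no distribution, so lognormal levels and a uniform percentage fall are assumptions from here on.

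**Step 3: within-patient SD on the log scale (SDlog).** The documents give none, and their figures disagree.
- Log SD of levels: √ln(1 + 0.8²) = 0.703.
- Correlation 0.7 on the raw scale: SDlog = √(2 × (0.4947 − ln(1 + 0.7 × 0.64))) = 0.50. At that value about 38% of untreated patients would change by more than 42% in either direction, and only 24% would be within 15%.
- A largest placebo change of 42%, if that group had 20–45 patients with one change each (assumption): SDlog about 0.16–0.30.

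So a range is shown.

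**Step 4: raw versus log power.** Bivariate lognormal, same margins under no effect, level SD 800, n = 20, two-sided 0.05, simulated.

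| SDlog | Fall | Raw | Log |
|---|---|---|---|
| 0.15 | 10% | 68% | 85% |
| 0.20 | 10% | 45% | 61% |
| 0.20 | 15% | 80% | 93% |
| 0.20 | 20% | 96% | 99.7% |
| 0.30 | 15% | 48% | 63% |
| 0.30 | 20% | 73% | 88% |
| 0.30 | 30% | 97% | 99.9% |
| 0.50 | 20% | 35% | 47% |
| 0.50 | 25% | 53% | 68% |
| 0.50 | 30% | 71% | 86% |
| 0.50 | 42% | 96% | 99.6% |

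At a 42% fall the loss is about zero for SDlog 0.15–0.30 and 3.6 points at 0.50. The peak is about 15–17 points, for falls of about 9–17% at SDlog 0.15–0.30 and about 20–30% at 0.50. With no effect, the raw test rejects in 4.1–4.3% of trials and the log test in about 5%.

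**Step 5: other error models, 42% fall, raw correlation about 0.69.**
- Independent log-scale error added at each visit: 88.0% raw, 98.3% log.
- Week 24 = 0.58 × baseline × lognormal error with mean one, SDlog 0.6: 89.5% raw, 99.9% log. The geometric mean fall here is 1 − 0.58 × exp(−0.18) = 52%, so part of the gap is a different target.
- The same, but with 42% as the median fall: 67.7% raw, 97.0% log. The mean fall is then only 1 − 0.58 × exp(0.18) = 31%.

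**Step 6: the reverse case.** If only patients at or above 600 pg/ml respond (pure assumption), SDlog 0.20 and a 20% fall give 81% raw and 73% log.

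**The case against.** The strongest reply is that the trial is powered for a fall of 42% or more, and there the raw test is adequate: at least 96% in the main model. For SDlog 0.15–0.30 the peak loss sits largely among falls that Section 5.2 would call stable, and Section 14 describes the study as exploratory. All of that stands. It makes this an improvement, not a repair.

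It is also fair that the evidence for skew is indirect. The 10.6% figure needs 800 to be the SD of levels, which is not how the plan labels it, though it is the only reading that gives the stated power. Nor is the log scale better in every case, as Step 6 shows. These limits argue for keeping the raw test alongside; they do not argue for leaving the scale unstated.

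A reader might cite Section 3.3 as precedent for a log-scale outcome, since it says "Each 1-unit increase in baseline log (VEGF-D) was associated with a baseline to 12-month change". It does not support that. There, log(VEGF-D) at baseline predicts change in lung function, and the VEGF-D response itself is reported as a reduction in mean levels. The rank test planned for the questionnaires is weak evidence too, because those are a different kind of measure.

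**Conclusion.** The point holds as one of efficiency and pre-specification. With lognormal levels (SD 800), a proportional effect and 20 patients, the raw test costs 0–4 points at the planned 42% fall and up to about 15–17 points for smaller falls. Where the loss peaks depends on both the size of the fall and SDlog. Two of the other error models, with the mean fall held at 42% or the levels at plan, give about 10 points at a correlation near 0.7, with raw power of 88–90%.

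Two stronger readings should be resisted. A reader might infer that the primary test is invalid, but its type I error is slightly below nominal. A reader might also take 17 points as a limit set by the documents. It belongs to one assumed model, and Step 5 shows that others go further.

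The SD label is a separate matter and is wrong as written: the stated inputs give 60.6% power, not 80%. A log transformation does not cure it.

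**What to change.** In Section 15 and the synopsis:
1. Make the week-24 versus baseline comparison, and the VEGF-D regression, repeated-measures and mixed models, primary on log(VEGF-D). Report the week-24/baseline geometric mean ratio with a 95% CI, expressed as a percentage change.
2. Keep the raw pg/ml paired t-test as a named sensitivity analysis. It also covers a response confined to patients with high baseline levels.
3. Relabel 800 as the SD at each visit (SD of difference about 620, power 82%), or, if it truly is the SD of the difference, restate the power as about 61%.
4. Give a log-scale SD of the difference with its source and a range, and reconcile the correlation of 0.7 with 42% as the largest placebo change.

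Items 1, 2 and 4 need wording only: no extra patients, visits or samples. So does item 3 if 800 is the per-visit SD; if it is the SD of the difference, 80% power for 420 pg/ml on the raw scale would need 31 evaluable patients. The cost of item 1 is a changed estimand, from a mean pg/ml difference to a geometric mean ratio, and up to about 8 points less power if only high-baseline patients respond.

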	
correlation between repeated measurements within the same patient.
 
Subjects will be evaluable for safety if they have received at least one dose of the study drug. The frequency, severity and duration of all adverse events, regardless of cause, will be recorded on the case report forms. The frequency and severity of adverse events will be calculated by patient, with each patient counted once using the most severe grade experienced. The duration of adverse events will be calculated by the number of days each event persisted. Adverse events will be tabulated by body system and by severity using the NCI Common Terminology Criteria for Adverse Events (CTCAE) v4.0, which can be obtained from the CTEP website: http://ctep.cancer.gov/reporting/ctc.html. Tables will be generated for all adverse events including those that are judged to be possibly, probably or definitely related to the drug. In order to assess the safety and adverse effect profile of resveratrol in LAM, we will assign a binary indicator variable to indicate a patient with or without adverse events. A multivariable logistic regression model will be used to assess of the effect of the covariates on the probability of having adverse events for patient with LAM. All interested factors will be adjusted in the logistic regression model. Model selection will be based on stepwise criterion when appropriate.
 
Lung function parameters (FEV1 and FVC) will be measured at the baseline visit, and at every in-person visit. DLCO will be measured at the baseline visit and the last study visit. Similar analysis plan as VEGF-D will be employed for the lung function parameters. We will use the following questionnaire-based assessments to determine the quality of life in this trial: St. George's Respiratory Questionnaire (SGRQ), EuroQOL scale, San Diego Shortness of Breath scale (SD-SOB), and A Tool to Assess Quality of Life in LAM (ATAQ-LAM). Written permission has been obtained to use all these questionnaires. The scores on each of these questionnaires will be calculated at baseline, and at every in-person visit. We will compare median values at baseline and 24 weeks with the Wilcoxon signed rank test for each of these scales.
 
The spirometry values will be expressed as mean <math>\pm</math> SD. All spirometry maneuvers will be checked for acceptability and reproducibility as specified in the ATS/ERS criteria by an expert pulmonary physiologist. The spirometry values obtained from maneuvers that do not satisfy the ATS/ERS criteria for acceptability will not be used in the primary analysis. If spirometric values meet the acceptability criteria but fail to satisfy the repeatability criteria, those values will be graded for quality, but will be included in the primary analysis. Overall compliance with weekly home spirometry will be recorded and reported as a percentage. Comparison of home spirometry and office-based spirometry values will be performed using the Bland-Altman method at baseline, and at each time frame that patients get an office-based spirometry (i.e. every 8 weeks). Rate of change of FEV1 (slope) over time will be calculated by using all available values (without imputations) in a linear mixed effects model after considering the correlation of the observations within each subject, and the time between measurements will be treated as a fixed effect. In

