### **14.4.2 Recording AEs**

Throughout the study all identified adverse events (serious and non-serious) will be recorded on all appropriate source document and adverse event case report forms regardless of their severity or relation to the study. A complete description of all adverse events will include event description, time of onset, investigator assessment of severity, relationship to study agent or procedures, time of resolution/stabilization of the event, expectedness, determination of whether the AE qualifies as a SAE, and action taken. A change in the severity of the AE will also be documented. Assessment of severity and relationship will be documented on the source documents or the on the CRF.

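### The stepwise logistic model for any adverse event, in at most 25 patients, is at high risk of having no finite estimates or selecting chance predictors

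*Combined protocol and SAP*

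**What the plan says.** Section 15, Specific Aim #2, introduces the model as its means of assessing the safety profile: "we will assign a binary indicator variable to indicate a patient with or without adverse events". A multivariable logistic regression then relates that indicator to covariates. Two sentences govern the covariates. The first is "All interested factors will be adjusted in the logistic regression model" and the second is "Model selection will be based on stepwise criterion when appropriate". The Data Analysis entry of the Protocol Synopsis carries the same text.

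The plan does not give the covariates, how many there are, the entry and stay levels, the direction of selection, what would make selection appropriate, or an exact or penalised fallback.

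The outcome is broad. Section 14.4.2 has AEs recorded "regardless of their severity or relation to the study". Section 14.3.1 includes abnormal laboratory findings, and section 14.3.3 includes a puncture-site bruise of more than 2 cm.

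Section 7.2 caps enrolment at 25. Everyone who takes at least one dose is in the safety set. The same Aim also plans descriptive output: frequency and worst grade per patient, duration, and tables by body system, CTCAE grade and relatedness.

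**The concern.** A logistic model draws its information from the smaller outcome group. If most patients have at least one AE in 24 weeks, that group is the handful without one. The coefficients are then poorly determined. Often some combination of covariates splits the two groups perfectly (separation), and the odds ratio runs to infinity. Choosing covariates by their p-values and then reading those p-values against 0.05 also overstates the evidence for whatever is chosen.

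The two governing sentences pull in different directions as well. Adjusting for every factor of interest is one procedure, and selecting among them is another. Each has its own way of failing.

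Safety is the first secondary endpoint (section 4.2). Section 3.6 says that no clinical data exist on the adverse-effect profile of resveratrol in LAM and that a multi-centre phase III trial is planned next. A chance risk factor or an infinite odds ratio could be carried into that trial. Meanwhile the quantity that matters most, the proportion of patients with events and its uncertainty, is given no interval.

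**Working it through.** **The plan's own figure.** The only sample-size statement concerns the primary endpoint: "a sample size of 20 subjects will provide 80% power to detect a mean VEGF-D difference". The step to enrolment reproduces: 20 / (1 − 0.20) = 25. The 20 reproduces if 800 is the SD of each measurement: 800 × √(2 × (1 − 0.7)) = 619.7, which gives 82.0% power two-sided. Read as the SD of the difference, as written, 800 gives 60.6%. That discrepancy is a separate matter and is not used here. No event count or precision target is given for the safety model.

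**Inputs**
- N = 25 (section 7.2).
- Significance level 0.05 (section 15). Its use as the entry level is an assumption.
- Any-AE rate: not stated for this trial. The one anchor is 57% with minor events in a volunteer study (section 9.1.2). I use 57%, 80%, 90% and 95%; the last three are assumptions.
- Candidate covariates: not stated. I assume 5 to 10, half binary and half continuous, all unrelated to the outcome.

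**Step 1: patients without an AE.** Expected number = 25 × (1 − rate). The chance that all 25 have an AE, so that no model exists, is rate^25.

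| Any-AE rate | Expected AE-free | AE-free per candidate, 5 candidates | Chance that all 25 have an AE |
|---|---|---|---|
| 57% | 10.75 | 2.2 | <0.001% |
| 80% | 5.0 | 1.0 | 0.4% |
| 90% | 2.5 | 0.5 | 7.2% |
| 95% | 1.25 | 0.25 | 27.7% |

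**Step 2: fitting all factors.** In simulated trials that contain both outcomes, a linear-programming check asks whether complete or quasi-complete separation exists, meaning no finite maximum-likelihood estimates. The lower figure is for 5 candidates and the upper for 10.

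| Any-AE rate | Full model separated |
|---|---|
| 57% | about 2-30% |
| 80% | about 23-75% |
| 90% | about 62-93% |
| 95% | about 83-99% |

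With 20 patients instead of 25, and rates from 57% to 95%, the ranges are 8-92% for 5 candidates and 69-100% for 10.

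**Step 3: selecting among factors.** A reference value is the chance that at least one of k independent null covariates has p < 0.05: 1 − 0.95^5 = 22.6% and 1 − 0.95^10 = 40.1%. In simulation, at least one noise covariate passes score-test entry at 0.05 in about 18-45% of trials at rates of 57-90%. Adding a Wald stay rule at 0.05 lowers this. For 5 and 10 candidates it becomes 18% and 36% at a 57% rate, 13% and 21% at 80%, 11% and 20% at 90%, and 9% and 17% at 95%.

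Steps 2 and 3 describe different procedures and should not be added together. A forward selection need never fit the full model. Simulation error is up to about 5 percentage points.

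**Step 4: what an interval would show.** With 0 events in 25 patients, the exact two-sided 95% upper limit is 1 − 0.025^(1/25) = 13.7%.

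**The case against.** The best defence is that little depends on this model. The AE tables by body system, grade and relatedness describe safety without it, and in an open-label single-arm trial that is the natural analysis. Section 14 calls the study exploratory. The stopping rules (sections 7.2 and 13.1.3), the resveratrol dose-reduction rules (section 12.3.2) and the primary analysis do not use the model. Stepwise selection is conditional on being judged appropriate, so an analyst could decline it. The high AE rates are assumed, and section 14.3.1 excludes conditions present at screening unless they worsen. At the documented 57% with 5 candidates, separation is rare.

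Most of this stands, and it limits the point. A reader might infer that the model is bound to fail or to name false predictors. The documents do not support that, because the result depends on an AE rate and a covariate count that they do not give. A reader might also infer that the safety aim cannot be met. That is wrong too, because the tables meet it descriptively.

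The defence does not remove the problem. The condition on stepwise selection is undefined, so it gives no protection. Declining selection leaves the adjustment for all factors, where separation is the greater risk. Even at 57%, 10 candidates give separation in about 30% of trials. The tables carry no confidence intervals, which leaves this model as the only inferential safety analysis.

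**Conclusion.** The point holds as a statement of risk. With at most 25 patients, an outcome that counts every event and an open covariate list, the planned model has a high risk of separation or chance predictors. The size runs from modest (57% AE rate, 5 candidates: separation about 2%, false entry about 18%) to severe (90% rate, 10 candidates: separation about 93%). If 95% of patients have an AE, there is a 28% chance that no model exists.

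These figures rest on assumed AE rates above 57%, on 5 to 10 null covariates and on entry at 0.05. The documents fix none of them, and that gap is itself part of the finding. The consequence is confined to misleading or inestimable odds ratios in the safety report. The primary result and the descriptive AE tables are unaffected.

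**What to change.** In section 15, Specific Aim #2, and in the Data Analysis entry of the Protocol Synopsis:

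- Delete the stepwise multivariable logistic model.
- Keep the planned AE tables. Add exact 95% confidence intervals to the per-patient proportions with any AE, any AE of grade 3 or higher, and any resveratrol-related AE.
- If a covariate question is kept, name one or two covariates in advance and examine them one at a time with Firth or exact logistic regression. Label this exploratory, and use related events or events of grade 2 or higher as the outcome in place of any AE.

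The cost is a change of wording and less analysis than now planned, with no new data or patients. The adjusted odds ratios are lost, but they would not have been reliable.
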